6.1 Risks

The Effects of Exenatide, a GLP-1 Agonist, on Alcohol Self-Administration in Heavy Drinkers
Version 1.8 10.5.20

To minimize the risk of adverse health events we will instruct subjects to contact study staff with any questions or concerns about changes in health effects after initiating study medication/placebo. Trained medical staff will evaluate any reported adverse effects and make a clinical determination about management. Subjects will be given a wallet card that includes a phone number with 24/7 coverage for medical emergencies.

C) Potential Risks

Risks of study medication

The following adverse reactions were observed in subjects treated with 10-20 mcg of exenatide per day. The package insert for the exenatide immediate release formulations lists the incidence of the following adverse reactions versus placebo as follows for patients receiving monotherapy with exenatide in diabetic subjects: Nausea (8% versus 0%), Vomiting (4% vs 0%), and dyspepsia (3% versus 0%)⁵⁶. Between one and two percent of Type II diabetic subjects receiving exenatide monotherapy experienced decreased appetite, diarrhea and/or dizziness. Type II diabetic subjects receiving combined therapy of exenatide with metformin (and/or sulfonylureas) experienced a higher incidence of adverse effects than did subjects receiving exenatide monotherapy. The incidence of adverse effects in patients receiving exenatide in combination with metformin or sulfonylurea versus those treated with placebo and these antidiabetic agents is shown in table 3.

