There is a warning that post-marketing data indicate that acute pancreatitis including necrotizing pancreatitis and hemorrhagic pancreatitis (fatal and non-fatal) have occurred in association with exenatide administration. A precaution exists stating that there is an increased risk of hypoglycemia occurring in patients taking exenatide in combination with sulfonylureas. The administration of pharmacologic doses of GLP-1 were not found to increase the incidence of occurrence of hypoglycemia in fasting healthy subjects⁵⁷. Exenatide may produce nausea and vomiting that can be problematic in patients with impaired renal function. This drug was not well tolerated in patients with end-stage renal disease who were undergoing dialysis. It is advised that exenatide be used with caution in patients with severe renal impairment. Some reports of allergic reactions have been reported during post-approval use of exenatide including injection-site reactions, generalized pruritus and/or urticaria, macular or papular rash, angioedema, anaphylactic reaction.

In a study of the effects of monotherapy with exenatide 10 mcg twice daily over a period of 24 weeks, 10% of subjects experienced nausea vs 0% of those who received placebo. Three percent of subjects vomited vs. 0% of those who received placebo⁵⁸. In one study 65% of healthy subjects developed nausea following injection of 10 mcg dose exenatide when they were allowed to eat a standardized meal 60 minutes after the administration of this drug⁵⁹. In a dose ranging study of exenatide monotherapy with type-2 diabetics, nausea was reported by 13% of subjects receiving .1 mcg/kg dose, 0% of subjects receiving .2 mcg/kg dose, 29% of subjects receiving .3 mcg/kg dose, 60% of subjects receiving .4 mcg/kg dose, and 14% of subjects receiving placebo⁶⁰. There is a warning that thyroid C-cell tumors have been observed to occur in female rats receiving extended release treatment with exenatide. Also, exenatide has produced developmental toxicity when administered to pregnant rats.

Table 3. Combination therapy vs. placebo		
Adverse effect	Placebo	Combination Therapy
Nausea	18%	44%
Vomiting	4%	13%
Diarrhea	6%	13%
Feeling jittery	4%	9%
Dizziness	6%	9%
Headache	6%	9%
Dyspepsia	3%	6%
Asthenia	2%	4%
Gastric Reflux	1%	3%
Hyperhidrosis	1%	3%

Risks of Phlebotomy, medication injection, and pinprick for blood glucose test

These procedures may cause pain, bruising, lightheadedness, fainting and on rare occasions, infection.

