Subjects will be given a priming drink designed to increase the subject's blood alcohol level (BAL) to 0.03g/dl, using the alcohol of their choice that is 24% Alcohol By Volume (ABV) or greater. Drinks will be mixed with a sugary mixer (3:1 Mixer:Alcohol) to preclude the occurrence of hypoglycemia. The volume of alcohol will be calculated using an online tool developed by UW-Madison (<http://dionysus.psych.wisc.edu/WebCMS/baccalc.htm>) based on a formula described by Watson⁵¹. The subjects will be asked to drink the priming drink over a period of 5 minutes. The purpose of the priming drink is to normalize drinking in the laboratory.

Absorption period. Subjects will be observed for 40 minutes following the priming dose of alcohol. This period will provide ample time for subjects to reach the target BAC. Breathalyzer readings will be completed at 10 minutes intervals.

Alcohol self-administration Blocks 1 and 2. In each of the alcohol self-administration Blocks, subjects will be presented with four drinks, each mixed to raise their BAC by 0.0125g/dl. They will be told that they can either consume the desired number of drinks over the following 60 minutes, or they will receive the equivalent dollar amount of the cost of each drink (\$3.00) they did not consume. At the end of each 1-hour session the drinks will be removed and the volume of alcohol remaining will be measured with a graduated cylinder. Cravings will be assessed using the AUQ and VAS every 30 min during the self-administration blocks. BAC levels will be obtained at the end of the Block 2 session as will blood glucose levels. Blood glucose levels will be measured at the end of Block 2 using a glucometer and blood obtained from a pinprick sample. If the subject is found to be hypoglycemic (glucose < 70 mg/dL), staff will give the subject orange juice and re-test in 30 minutes. If the subject is found to be hyperglycemic (glucose > 300 mg/dl), staff will escort the subject to the BMC emergency department for evaluation. At the end of this session subjects will also be asked to rate their experience of nausea using a visual analog scale developed to assess nausea in an emergency department⁵². Subjects will be assessed for safety prior to subjects leaving the laboratory. Subjects will not be released until their BAC is below 0.04 g/dl and they are not behaviorally impaired.

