12.1 Study Hypotheses and Planned Analyses

For our primary outcomes, data from subjects who experience moderate to severe nausea during the alcohol self-administration trials will be excluded from our statistical analysis. Although the dosing chosen for this study minimizes the potential for nausea as a medication side effect, this may occur in some subjects. These subjects will be excluded from analyses as medication-induced nausea could confound the drinking outcomes. The presence of nausea will be established by a rating greater than 30 on a VAS scale that rates nausea from no nausea to unbearable nausea⁵³.

Hypothesis	Proposed Analyses
1. Subjects will consume less alcohol during an alcohol Challenge Trial when receiving exenatide	The volume of alcohol consumed during alcohol challenge trials 1 and 2 will be used to test the effect of exenatide on alcohol consumption. We will use a mixed

The Effects of Exenatide, a GLP-1 Agonist, on Alcohol Self-Administration in Heavy Drinkers
 Version 1.8 10.5.20

compared to when they receive a sham injection.	models repeated measures approach to test for differences between alcohol consumption between the exenatide and sham injection self-administration trials ⁵⁴⁻⁵⁵ . This data will be divided into first and second-hour blocks of self-administration. Within-subject factors for this analysis will include Treatment and Time Block. Trial order will be used as covariate in these analyses to allow evaluation as to whether the order of treatments had a significant effect on the outcome. Appropriate covariance structures will be determined using Akaike's information criteria to evaluate the best model fit. Results analysis will be examined for both treatment effects and the Treatment x Time Block interaction results.

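### The primary consumption and craving analyses drop subjects for nausea rated after dosing, and no analysis of all randomised subjects is planned beside them

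*Combined protocol and SAP*

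**What the plan says.** Section 12.1 opens with the analysis set for the primary outcomes: "data from subjects who experience moderate to severe nausea during the alcohol self-administration trials will be excluded from our statistical analysis". The reason given is that "These subjects will be excluded from analyses as medication-induced nausea could confound the drinking outcomes". The threshold follows: "The presence of nausea will be established by a rating greater than 30 on a VAS scale". Section 4.2.1 names consumption and craving as the primary outcomes, so the rule covers Hypotheses 1 and 2 and leaves Hypotheses 3 and 4 alone.

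On timing, Sections 8 and 9 place the injection 30 minutes before the priming drink. Section 9, under the self-administration blocks, says of the nausea rating: "At the end of this session subjects will also be asked to rate their experience of nausea using a visual analog scale". Appendix B lists a nausea VAS at the end of Block 1 and at the end of Block 2, and none before dosing.

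The documents define no all-randomised analysis set for H1 or H2 and plan no sensitivity analysis that keeps subjects with nausea. Section 12.2 plans for 15–20% non-completion (36 randomised, 28 completers) and does not mention nausea exclusions.

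**The concern.** A confounder is a common cause of treatment and outcome. In this crossover the order of treatment is randomised, and nausea is measured after the injection and after drinking. If the drug causes the nausea, as Section 12.1 says it may, nausea is a consequence of treatment and possibly part of how the drug changes drinking. With no pre-dose rating, the rule also cannot separate nausea due to the drug from nausea due to the alcohol consumed, and the amount consumed is the H1 outcome.

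The analysed set therefore depends on what happened after treatment, and the resulting bias has no fixed sign:

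- If the subjects who become nauseated are those who cut down most on exenatide, removing them dilutes the estimate.
- If nausea becomes more likely the more a subject drinks on exenatide, removing them takes out people who drank a lot on the drug and inflates the reduction.
- If nausea is unrelated to the individual drug effect, nothing shifts.

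With only the excluded-set result, a reader cannot tell which case applies.

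The rule is also not fully stated. It reads most naturally as removing the whole subject for nausea in either trial, but does not say so. Nor does it say which of the block ratings counts.

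**Working it through.** **Inputs from the documents.** Section 12.2: reduction 1.5 drinks, SD of the between-trial difference 2.1, effect size 0.7, alpha 0.01, power 0.81, 28 completers, 36 randomised, 15–20% non-completion. Section 6.1, rates of any nausea:

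- "Nausea (8% versus 0%), Vomiting (4% vs 0%), and dyspepsia (3% versus 0"%) on monotherapy at 10–20 mcg per day;
- 10% versus 0% at 10 mcg twice daily over 24 weeks;
- from the dose-ranging study, "nausea was reported by 13% of subjects receiving .1 mcg/kg dose, 0% of subjects receiving .2 mcg/kg dose", then 29% at .3 mcg/kg, with 14% on placebo;
- in one study, "65% of healthy subjects developed nausea following injection of 10 mcg dose exenatide when they were allowed to eat a standardized meal".

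**Which rates apply.** The rate of VAS above 30 after 5 mcg with alcohol is not given. A fixed 5 mcg equals .1 mcg/kg at 5/0.1 = 50 kg, .2 at 5/0.2 = 25 kg and .3 at 5/0.3 = 16.7 kg. At an assumed 100 kg it is .05 mcg/kg. The 29% and 65% figures thus belong to higher doses and are stress cases only. I use 8–10% as a working range.

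**1. The plan's own figure.** Paired t-test, noncentral t, two-sided alpha 0.01 (sidedness is not stated; two-sided reproduces the figure). With n = 28 and d = 0.7, power is 0.815. The stated 0.81 is reproduced.

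**2. Room for exclusions.** Expected completers are 36 × 0.80 = 28.8 to 36 × 0.85 = 30.6. The share that can be dropped before n falls below 28 is 1 − 28/28.8 = 2.8% to 1 − 28/30.6 = 8.5%.

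**3. Power after exclusion.**

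| Excluded | n left | Power, d = 0.7 | Power, d = 1.5/2.1 = 0.714 |
|---|---|---|---|
| 0% | 28.8–30.6 | 0.83–0.86 | 0.85–0.88 |
| 8% | 26.5–28.2 | 0.79–0.82 | 0.81–0.84 |
| 10% | 25.9–27.5 | 0.77–0.81 | 0.79–0.83 |

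**4. Shift if nausea goes with a larger drug effect.** Assume that a normal nausea tendency has correlation r with the individual reduction, and that the top fraction p is removed. The mean reduction among those kept falls by

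r × 2.1 × φ(z)/(1 − p), with z = Φ⁻¹(1 − p).

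- p = 0.08: z = 1.405, φ(z) = 0.1487. Shift 0.102 at r = 0.3 and 0.170 at r = 0.5.
- p = 0.10: z = 1.282, φ(z) = 0.1755. Shift 0.123 at r = 0.3 and 0.205 at r = 0.5.
- r = 0.1 gives 0.03–0.04; r = 0 gives zero.

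Against 1.5 drinks, 0.102/1.5 = 7% and 0.205/1.5 = 14%.

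To judge how strong r = 0.3–0.5 is: the gap in mean reduction between removed and kept subjects is r × 2.1 × φ(z)/[p(1 − p)], or 1.2–2.1 drinks over these cases.

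**5. Shift in the other direction.** Simulation of 400,000 pairs with 0–8 drinks, between-trial correlation 0.54, SD of the difference 2.1 and no true drug effect. The log-odds of nausea are assumed to rise by 0.2–0.5 per drink taken on exenatide. The spurious reduction is 0.03–0.07 drink at 8% excluded and 0.04–0.09 at 10%. With slope zero it is about zero.

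**The case against.** The exclusion is a stated scientific choice: fixed in advance, with a numeric threshold, a reason and a limited scope. In a laboratory proof-of-concept study, asking whether exenatide lowers drinking and craving in people it does not make sick is legitimate, and less drinking caused by nausea would not show an effect on alcohol reward. Whole-subject removal keeps the within-subject comparison. This stands, and it means the exclusion analysis should be kept. It does not justify leaving it as the only H1/H2 estimate.

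The size can also be challenged, and much of that stands. The correlations and slopes are not in the documents. A correlation of 0.3–0.5 means that removed subjects cut down by 1.2–2.1 drinks more than the others, about as much as the whole planned effect. Even then the shift is a quarter to half of one standard error (2.1/√28 = 0.40). The VAS above 30 rate is unknown, and Section 12.1 says "Although the dosing chosen for this study minimizes the potential for nausea as a medication side effect, this may occur in some subjects". At the unrounded effect size of 0.714, power stays at 0.79–0.84 for 8–10% excluded, so power loss is a minor part of the point.

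Finally, the rating rule can be read as any rating in either trial, and Section 9 can be read as compatible with Appendix B. That makes those items requests for clarification.

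**Conclusion.** The concern holds. The primary H1 and H2 analyses select on a rating taken after dosing and drinking, which the plan itself links to the drug, and no model keeps the excluded subjects. The likely effect is modest. At 8–10% excluded, the estimate is diluted by 0.10–0.20 drink if the correlation between nausea and drug effect is 0.3–0.5, or a reduction is inflated by 0.03–0.09 drink if nausea rises with drinking on exenatide. It is zero if nausea is unrelated to the individual effect. These figures rest on an assumed exclusion rate and an assumed link between nausea and drinking, neither of which the documents supply. The sample size does not mention these exclusions and leaves room for only 2.8–8.5% of expected completers. This should be fixed because it concerns the primary estimate and costs little; confidence in its size is medium.

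**What to change.** In Section 12.1:

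1. Pre-specify the H1 and H2 mixed models in all randomised subjects with outcome data, whatever their nausea rating. Report them with equal prominence beside the analysis that excludes VAS above 30. Making them primary would be preferable but is not essential.
2. If the exclusion analysis stays primary, state that its target is the effect in subjects without nausea above the threshold.
3. State whether nausea in either trial removes the whole subject, and which rating counts.
4. Report nausea ratings and the number above 30 by treatment.
5. Reconcile the nausea rating times in Section 9 and Appendix B.

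The cost is SAP wording and one further model run per outcome; nausea is already rated in both trials. The drawback is that the all-randomised estimate includes any reduction in drinking that works through nausea. The exclusion analysis beside it addresses that question.

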8 Study Intervention

Study Medication

Study medication will be purchased by the BMC Investigational Pharmacy Service. Medication will be administered using a 250mcg/mL, 5mcg/dose, 60 doses/pen, 1.2mL prefilled pen. Subjects will receive either a 5 mcg dose of immediate release exenatide or a sham injection. The 5mcg dose of exenatide is approved as the first dose to be administered to patients at the start of their treatment with this drug for FDA-approved indications. The sham injection will be a needle stick insulin syringes with pre-affixed needles as a sham syringe. No fluid will be injected as a protection for maintaining the blind. Note that the volume of fluid injected for a 5mcg dose is only 0.02ml. We do not expect that subjects will sense this volume of fluid (or lack thereof) during the injection. Subjects will be shielded from seeing the injection to maintain the blind. The individual who administers medication will not participate in subject evaluation to maintain

The Effects of Exenatide, a GLP-1 Agonist, on Alcohol Self-Administration in Heavy Drinkers

Version 1.8 10.5.20

the study blind. The study medication will be administered subcutaneously 30 minutes prior to the priming dose of alcohol.

Dosing

Subjects will receive either a 5 mcg dose of immediate release exenatide or a sham injection on both alcohol challenge days.

Medication Storage

Medication will be stored in the Investigational Pharmacy under refrigerated conditions and may be stored at room temperature for up to 30-days following dispensing. Medication will be stored in a secured area until the time that medication is needed for study subjects. Stability and expiry will be monitored by IPS according to the labelling of the medication from the manufacturer.

Randomization

Study randomization will be performed by IPS using a stratified block randomization procedure. The study statistician will provide IPS with a randomization log. On the day of randomization, study staff will provide IPS with a randomization number based on the stratifying variable (heavy vs very heavy drinking) and IPS will determine the order of drug vs. sham exposure based on the randomization log.

Medication Labeling

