The study number will be preprinted on each injection pen. The label will include the drug name the subject number, storage conditions, the 24/7 phone number of the clinical site, and places to record the subject number and the date dispensed. Additional fields may be added to this label to meet any regulatory requirements as determined by IPS.

Medication Blinding/unblinding

Study medication will not be blinded. Medication will be administered by GCRUstaff who are not part of study staff who perform data collection. The Study PI and study staff will be blinded to study medication. The PI and study physician(s) will make the decision to un-blind the identity of the study medication in the event that the study blind needs to be broken to make medical decisions regarding subject treatment.

Medication accountability

The site principal investigator (PI) or designated study personnel will maintain a log of all study medication and record of dispensing of all medication to the subject.

9 Study Procedures

Study Overview: Each subject will complete 3 clinic visits over a period of up to 28 days of participation. Study participation is comprised of a baseline assessment, alcohol challenge Trial #1, and alcohol challenge Trial #2.

Baseline assessment: Prior to the visit, subjects will complete a COVID-19 symptom screening questionnaire following standard of care procedures. If the subject does not complete the screening questionnaire before arriving in clinic, study staff will administer the questionnaire outside of the clinic at a 6-foot distance. If the subject answers 'yes' to any question about known COVID symptoms, their in-clinic visit will be cancelled and they will be advised to contact their PCP and/or get tested at a testing center. Consenting subjects will undergo a general medical screen, physical examination, and electrocardiogram. Drinking will be assessed using

The Effects of Exenatide, a GLP-1 Agonist, on Alcohol Self-Administration in Heavy Drinkers
Version 1.8 10.5.20

the Time-Line Follow-Back (TLFB)⁴⁵, and alcohol withdrawal using the Clinical Institute Withdrawal Assessment (CIWA)⁴⁶. Exclusionary mental health conditions will be assessed using the MINI Neuropsychiatric Interview for DSM-5⁴⁷. Subjects will undergo laboratory testing that includes liver and renal function tests, glucose, serum lipase, complete blood count, urine toxicology and a urine pregnancy test for women of child bearing potential.

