Study randomization: Subjects will be randomized to a crossover sequence of drug exposure. Subjects will be assigned to one of two groups, with one group receiving exenatide in the alcohol challenge Trial #1 and the other receiving exenatide prior in the alcohol challenge Trial #2. Randomization of subjects will be accomplished using a stratified randomization procedure that will allow for between-group balance for drinking status (heavy vs. very heavy). Heavy drinking is defined as ≥ 21 and < 35 standard drinks per week for men, and ≥ 14 and < 28 standard drinks per week for women. Very heavy drinking is defined as ≥ 35 standard drinks per week for men, and ≥ 28 standard drinks per week for women. This stratified randomization will minimize the possibility that the order of study drug administration seems to influence outcomes when order effects are actually related to differences in severity of drinking between the two groups of subjects who are receiving the study medication in a different order. On the day of randomization, subjects will undergo an alcohol breath test, urine drug screening, assessment of concomitant medications, and the TLFB. Subjects who have purposefully abstained from drinking and achieved 14 days of abstinence prior to the challenge will be discontinued from participation for ethical reasons⁴⁹.

Alcohol Challenge Trials 1 & 2: Subjects will return to the laboratory within 14 days of the baseline assessment to complete the alcohol Challenge Trial #1. Prior to the visit, subjects will complete a COVID-19 symptom screening questionnaire following standard of care procedures. If the subject does not complete the screening questionnaire before arriving in clinic, study staff will administer the questionnaire outside of the clinic at a 6-foot distance. If the subject answers 'yes' to any question about known COVID symptoms, their in-clinic visit will be cancelled and they will be advised to contact their PCP and/or get tested at a testing center. Concomitant medications, urine drug screening, Blood Alcohol Concentration (BAC) will be assessed to determine eligibility to proceed with the challenge. A BAC reading of 0.000 is required at each visit to continue with the study procedures. For safety reasons, subjects will be asked to arrange transportation plans that does not include driving themselves home.

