2. Subjects will report lower levels of craving as measured by the Visual Analog Scale (VAS) and the Alcohol Urge questionnaire (AUQ) during the exenatide Challenge Trial compared to the sham injection Challenge Trial.	Craving measures (AUQ and VAS) collected at 30-minute intervals during the self-administration trials will be used to test the effect of exenatide on alcohol craving. A mixed models approach will be used to test for differences in craving between the exenatide and sham injection Challenge Trials. Within-subject factors for this analysis will include Treatment and Time Block. Trial order will be used as covariate in these analyses to allow evaluation as to whether the order of treatments has a significant effect on the outcome.
Hypothesis 3: Areas under the breath alcohol concentration curves (AUC's) in heavy drinkers obtained during the first 40 minutes after ingestion of the priming drink of alcohol will be significantly lower in subjects when they receive exenatide as compared to when they are given sham injections	AUC's for BAC obtained using data obtained during the 40-minute absorption period will be compared between Challenge Trials using a repeated measures mixed models approach. In addition, individual BAC values obtained at 10-minute intervals after alcohol ingestion of the priming drink also will be compared between the sham injection and exenatide treatment trials using a repeated measures mixed models approach. A significant time x trial interaction value also will be taken to indicate a significant between trial difference in the rates of alcohol absorption.
Hypothesis 4. The proportion of subjects with post-trial blood glucose levels in the hypoglycemic range will not differ significantly between the sham injection and exenatide trials.	The proportion of subjects with blood glucose values below 50 mg/dl will be compared within subjects using the McNemar's test. We hypothesize that there will be no difference in blood glucose levels between the alcohol Challenge Trials.

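### The crossover models never name Period (Trial 1 vs Trial 2): Trial order is uncoded for Hypotheses 1 and 2, and Hypothesis 3 has no order term at all

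*Combined protocol and SAP*

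**What the plan says.** Section 9 (Study randomization) describes two groups, one given exenatide at Trial 1 and the other at Trial 2.

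- **Hypothesis 1 (volume consumed), Section 12.1:** "Within-subject factors for this analysis will include Treatment and Time Block. Trial order will be used as covariate in these analyses". Time Block is the first or second hour within a session. The plan adds: "Results analysis will be examined for both treatment effects and the Treatment x Time Block interaction results".
- **Hypothesis 2 (craving):** the same factors, and "Trial order will be used as covariate in these analyses to allow evaluation as to whether the order of treatments has a significant effect".
- **Hypothesis 3 (breath alcohol):** AUCs from the 40-minute "absorption period will be compared between Challenge Trials using a repeated measures mixed models approach". For the 10-minute readings, "A significant time x trial interaction value also will be taken to indicate a significant between trial difference in the rates of alcohol absorption". 'Trial' here contrasts sham with exenatide, so it is the treatment factor. Neither model names order, period or sequence.

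The coding of Trial order is not given, and the rest of the protocol points both ways:

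- **Sequence.** The Randomization text in Section 8 says "IPS will determine the order of drug vs. sham exposure based on the randomization log". Section 9 justifies stratification by the possibility that "order effects are actually related to differences in severity of drinking between the two groups of subjects".
- **Session number.** Section 9 (Study Overview) lists "baseline assessment, alcohol challenge Trial #1, and alcohol challenge Trial #2", so 'Trial' with a number is the protocol's label for a session.

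**The concern.** In a 2x2 crossover, a change between sessions (familiarity with the laboratory, learning about the cash alternative, a drift in drinking) adds to the treatment difference in one sequence and subtracts from it in the other. If Period is not in the model, that change goes into the residual and enlarges the standard error even when the sequences are equal in size. When they are unequal, part of it also goes into the treatment estimate.

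The label Trial order suggests that this has been dealt with. Under the sequence reading it has not. Sequence is a between-subject term and cancels out of every complete pair. Two analysts could each follow the plan and report different estimates.

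The interaction tests have the same gap one level down. If the session change differs between the first and second hour, only a Period-by-time term removes it. A Period main effect does not.

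**Working it through.** **Inputs.** From Section 12.2: effect 1.5 drinks, SD of the between-trial difference 2.1, alpha 0.01, power 0.81, 28 completers of 36 randomized, 15-20% non-completion. Assumption: the documents give no Trial 1 to Trial 2 shift, so p = 0.5, 1.0 and 1.5 drinks are illustrative. The largest equals the whole assumed treatment effect.

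**Plan's own figure.** A paired t-test with d = 0.7, n = 28 and two-sided alpha 0.01 has power 0.815, and n = 27 gives 0.796, so 28 reproduces. With d = 1.5/2.1 = 0.714, power is 0.834.

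**Estimates.** Let D be sham minus exenatide, and let p be the fall in drinking from Trial 1 to Trial 2. Then D has mean 1.5 + p in the sham-first group (n1) and 1.5 - p in the exenatide-first group (n2).

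- No Period: the estimate is the overall mean of D, with expectation 1.5 + p(n1 - n2)/n.
- With Period: the estimate is the average of the two sequence means, with expectation 1.5.
- At 12/16 and p = 1: 1.5 - 4/28 = 1.357. At 16/12: 1.5 + 4/28 = 1.643.

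**Standard errors at 14/14, p = 1, SD 2.1.**

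- With Period: (2.1/2) x sqrt(1/14 + 1/14) = 0.397.
- Without: sqrt[(2.1^2 + 1^2 x 28/27)/28] = sqrt(5.447/28) = 0.441, about 11% larger.

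**Power by simulation** (200,000 runs per scenario, two-sided alpha 0.01). Without Period the test is a one-sample t on D. With Period it uses the pooled within-sequence SD on 26 df. Section 12.2 does not say whether 2.1 is net of a session shift, so both readings are shown. 'Total' uses a residual SD of sqrt(2.1^2 - p^2).

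| Split (sham-first/exenatide-first) | p | Net SD: without vs with Period | Total SD: without vs with Period |
|---|---|---|---|
| 14/14 | 0.5 | 0.81 vs 0.83 | 0.84 vs 0.86 |
| 14/14 | 1.0 | 0.75 vs 0.83 | 0.86 vs 0.93 |
| 14/14 | 1.5 | 0.64 vs 0.83 | 0.90 vs 0.99 |
| 12/16 | 1.0 | 0.64 vs 0.82 | 0.76 vs 0.92 |
| 16/12 | 1.0 | 0.84 vs 0.82 | 0.93 vs 0.92 |

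At 16/12 the unadjusted test gains slightly in power only because the effect is overstated.

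**How often the sequences are unequal.** If 28 of 18 + 18 are retained at random (hypergeometric), a 16/12 or worse split in either direction has probability 0.23. The mean absolute bias is then 0.03, 0.07 and 0.10 drinks for the three shifts, which is 2-7% of 1.5.

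**Type I error without Period.** At 14/14 under the net reading it falls to about 0.008, 0.005 and 0.002. It exceeds 0.01 only at rare splits: about 0.016 at 10/18 with p = 1, and that split has probability 0.0014 each way.

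**Does a sequence covariate help?** Model fit at 12/16 with p = 1: the estimated reduction is 1.357 with no order term, 1.357 with sequence and 1.500 with Period.

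**Interaction test.** With the 1-drink shift confined to the second hour at 12/16, Treatment x Time Block is off by 1 x 4/28 = 0.143 drinks with no order term, with sequence, and with a Period main effect. It is off by 0.000 only with Period x Time Block.

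**Hypotheses 2 and 3.** The documents give no SD or shift for craving or AUC, so only SD units of the paired difference are possible. For shifts of 0.1, 0.25, 0.5 and 1.0 SD, the unadjusted standard error at 14/14 is larger by a factor sqrt(1 + p^2 x 28/27), that is by 0.5%, 3%, 12% and 43%. The bias at 12/16 is 0.01, 0.04, 0.07 and 0.14 SD.

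**The case against.** For the primary outcomes the defect is conditional. An order covariate is in the plan, and if it means session number, the main-effect analyses of Hypotheses 1 and 2 already contain Period. That stands: the documents favour the sequence reading but do not settle it.

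The size rests on an assumed shift. At 0.25 drinks and 14/14, power is 0.83 either way. At 0.5 drinks under the net reading it is 0.81, the planned value. Under the total reading, power at 14/14 without Period stays above plan throughout, so the loss there is precision forgone. Bias is zero at balance and small on average, and the test is usually conservative. All of this stands.

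The nausea exclusion should not be leaned on. It applies to the primary outcomes only, so it cannot unbalance Hypothesis 3. Every completer receives exenatide once, so nothing suggests that it favours one sequence. This is accepted, but random non-completion is enough to produce unequal sequences, and the loss of precision needs no imbalance.

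Hypothesis 3 is secondary, follows a formula-calculated priming drink and starts from a BAC of zero, so a session shift may be small. That limits the likely size. It does not explain why the order term given for Hypotheses 1 and 2 is missing here. The interaction error is zero with equal sequences, so that part of the fix matters least.

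**Conclusion.** The concern holds as an inexpensive improvement that should be made; it does not threaten the trial's validity. Under the better-supported sequence reading of Trial order, and for Hypothesis 3 as written, the planned contrast is less precise than the design allows if there is any session shift. It is modestly biased, in either direction, when the analysed sequences differ in size. For a 1-drink shift at balance, the power difference is 0.08 if the SD of 2.1 is net of the shift and 0.07 if it includes it. Only in the first case does power fall below the planned 0.81.

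These sizes depend on the assumed shift, two-sided alpha 0.01, 28 complete pairs and a shift that adds equally in both sequences. If Trial order means session number, what remains is Hypothesis 3 and the two interaction tests.

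**What to change.** In Section 12.1:

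- State that the models for Hypotheses 1, 2 and 3 include Period (Trial 1 vs Trial 2) as a fixed within-subject effect, with subject as a random effect.
- Add Period x Time Block, or Period x time, wherever Treatment x Time Block or time x trial is tested.
- Define Trial order. If it is session number, say so and name it for Hypothesis 3 too. If it is sequence, keep it in addition to Period.
- Report the number analysed in each sequence.

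The change is one or two sentences, best settled before unblinding. It uses one degree of freedom for Period and one for Period x Time Block with two blocks (three if four 10-minute BAC readings are modelled). If there is no session shift, the Period main effect lowers power from 0.834 to 0.831 at 14/14, to 0.822 at 12/16 and to 0.792 at a rare 10/18 split. Averaged over splits, the loss is about 0.6 percentage points (0.833 to 0.827). The planned 28 completers and the conduct of the study do not change.
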